# **The Use of Acellular Dermal Matrix in One-Stage Implant Breast Reconstruction: A Multicenter, Randomized, Controlled Trial (Multi-centered Canadian Allograft Trial-MCCAT)**

## **Study Protocol and Statistical Analysis Plan**

**Jun 15, 2011**

## i. SPECIFIC AIMS

We are currently leading a multi-center randomized controlled trial (RCT) to study the impact of acellular dermal matrix (ADM) assisted one-stage implant reconstruction on quality of life and patient satisfaction. This trial was awarded funding by ASPS-PSEF in 2009 and has been actively accruing participants at two breast centers in Toronto, Canada since September 2009. To date, 67 patients have been successfully enrolled into the RCT and an interim analysis has revealed similar short-term complication rates between the one-stage ADM implant study arm and the two-stage TE/I control arm. To increase patient enrollment into the trial, we plan to open trial recruitment to Vancouver General Hospital, the highest volume breast cancer center in western Canada in January 2011. In addition, by eliminating the intermediate inflation process and a second operative procedure, we hypothesize that both the cost and its utility as valued by patients will be superior in the one-stage ADM method compared to the two-stage TE/I method. In addition to measuring postoperative morbidity and complications, patient perception of their health status (utility) is a paramount consideration in the cost effectiveness analysis (CEA). CEA will be performed on person-level cost (direct and indirect) and effect data (utility measured by Breast Q© and EQ-5D) using net benefit regression, a novel technique developed by our collaborator ([name]). A preliminary cost comparison that was performed for 10 randomly selected patients in our RCT has demonstrated that the average cost was \$1,572 and \$595.91 more expensive per patient for the two-stage TE/I than the ADM assisted one-stage method for unilateral and bilateral reconstructions respectively at University Health Network. The addition of a CEA follows the natural progression of scientific research and is the logical sister study to assess the resource costs of this new surgical intervention in the current climate of increasing resource restraints and financial responsibilities.

The **primary objective** of this study is:

1. To compare patient satisfaction and QOL between one-stage ADM and two-stage TE/I reconstruction without ADM following mastectomy. Patient satisfaction will be evaluated using the Breast Q© at two-weeks, as well as six months and one year following completion of reconstruction.

**Hypothesis:** Patient satisfaction and QOL will be higher in the ADM assisted one-stage implant reconstruction group compared to the two-stage TE/I group at all three time-points.

The **secondary objectives** of this study are:

1. To compare the short- and long-term complication rates between the two techniques.

**Hypothesis:** The use of ADM in one-stage prosthetic breast reconstruction is not associated with increased short- and long-term postoperative complications compared with the traditional two staged TE/I procedure.

2. To examine the overall aesthetic outcome achieved using the ADM facilitated one-staged breast reconstruction at six months and one year following completion of the reconstruction.

**Hypothesis:** The overall aesthetic outcome achieved using the ADM facilitated one-stage breast reconstruction is superior to that following the two-stage breast reconstruction.

3. To perform a cost-effectiveness analysis (CEA) of the two reconstruction methods using the net benefit regression model on person-level cost and effect data collected during the study.

**Hypothesis:** Both the direct and indirect cost will be reduced and patient-reported utility will be greater for the one-stage ADM method compared to the TE/I method.

## ii. RESEARCH STRATEGY

### iia. Significance

Breast reconstruction has been shown to have a positive impact on the self-esteem and quality of life (QOL) in women suffering from breast cancer. The American Society of Plastic Surgeons has found the two-stage tissue expander/implant (TE/I) technique to be the most commonly used method of breast reconstruction. The wide-spread acceptance of the two-stage reconstruction is due to the high complication rates (25% overall explantation rate) associated with the traditional method of one-stage immediate implant reconstruction. The primary drawback to the TE/I technique is that it requires two separate operations under general anesthesia and multiple clinic visits for expander inflation. We are currently leading a multi-center randomized controlled trial (RCT) to study the impact of acellular dermal matrix (ADM) assisted one-stage implant reconstruction on QOL and patient satisfaction. This trial was awarded funding by the ASPS-PSEF and has been actively accruing participants at two breast centers in Toronto, Canada since September 2009. Our primary hypothesis is that the ability to convert a conventionally two-stage procedure to only one step would not only theoretically improve patient satisfaction, decrease the morbidity associated with multiple expansions and a second operation, but justify the prohibitively high cost of this new biomaterial incurred by the patient, hospital or insurance company.

Therefore, in addition to continuing our rigorous investigation of ADM in one-stage breast reconstruction in a multi-center, randomized controlled trial on patient satisfaction and quality of life measured using the Breast Q©, we propose to expand the scope of our current project to include a **cost-effectiveness analysis**. By eliminating the intermediate process of tissue expansion and converting the conventional two-stage procedure to one-stage with the use of human acellular dermis, we hypothesize that in addition to the cost of the new surgical treatment being lower, its utility will also be found to be greater compared to the two-stage TE/I breast reconstruction method. The addition of a cost-effectiveness analysis to our current RCT follows the natural progression of scientific research and is the logical sister study to assess the resource costs of this new surgical intervention. Furthermore, to increase patient enrollment into the trial, we are seeking funds from ASPS-PSEF to add a third site, Vancouver General Hospital which has the highest volume of immediate prosthetic breast reconstruction in Western Canada. With the addition of this third Canadian site, we anticipate fulfilling patient enrollment of a minimum of 72 patients per arm of the study by August 2011.

### iia – 1. Rationale for conducting a cost-effectiveness analysis

The heightened awareness in recent years of the need to operate within budgets in the health care sector has created the ideal climate for conducting cost-effectiveness analysis (CEA). This is especially true for reconstructive surgery of the breast following mastectomy due to the large number of available techniques used. Furthermore, the success of plastic and reconstructive surgeries is measured only in a small degree by post-operative complications and morbidity but to a greater degree in terms of patient perception of their health outcome (utility). Paramount in the CEA, therefore, is considerations of patient satisfaction and quality of life. By eliminating the intermediate process of tissue expansion and a second operative procedure, we hypothesize that both the cost and its utility as valued by patients will be superior in the one-stage ADM method compared to the two-stage TE/I method. Cost effectiveness analysis will be performed on person-level cost and effect data using net benefit regression, a technique developed by our collaborator.([name]) The cost data will come from hospital cost accounting systems and patient reports. The primary patient outcome measure will be the global Breast Q score and the secondary outcome measure will be quality adjusted life years (QALY) as measured by the EQ-5D. Our collaborator, [name] and his research team have extensive experience with applying standard CEA methods as well as developing new CEA methods.

## **iia – 3. Preliminary Data**

Since our trial opened recruitment at University Health Network and Women's College Hospital, Toronto, Canada in September 2009, a total of 67 women have been registered into the trial. Fifty-one patients have been randomized to date, and the other 16 patients are still awaiting randomization. Randomization has been balanced between the one and two-stage procedure arms in blocks of eight and is stratified by study site as well as laterality of the reconstruction. Breakdown of patients randomized by site and laterality is outlined below:

University Health Network (N=33)	Unilateral	Bilateral
1 stage w/ AlloDerm/ Implant (N=17)	(n=7)	(n=10)
2 stage w/ TE (N=16)	(n=8)	(n=8)

Women's College Hospital (N+18)	Unilateral	Bilateral
1 stage w/ AlloDerm/ Implant (N=10)	(n=2)	(n=8)
2 stage w/ TE (N=8)	(n=2)	(n=6)

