### iic. Approach

#### iib-1. Study Design

This **multi-center randomized controlled trial** will evaluate the impact of implantable human cadaveric acellular dermal matrix in the setting of immediate one-stage implant breast reconstruction. Three separate sites will participate in the trial (University Health Network, Women's College Hospital, and Vancouver General Hospital). Institutional Research Ethic Board approval has been obtained for all three sites.(APPENDIX 2) After obtaining informed consent and confirming eligibility both pre- and intra-operatively, patients will be registered in the study. Patients will be enrolled until there are 72 evaluable patients enrolled in each study arm. Stratification will be performed based on the laterality of the reconstruction (unilateral vs. bilateral reconstruction) at each of the three study sites. Patients who are deemed eligible pre-operatively by the investigating surgeon for the study will be **randomized** to undergo either **one-stage permanent prosthetic placement** with the use of implantable **acellular dermal matrix** or the conventional **two-stage TE/implant procedure** without the tissue substitute.

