#### Subject Exclusion Criteria

- Patients who undergo therapeutic or completion axillary lymph node biopsy
- Patients who have significant mastectomy flap ischemia or asymmetry between the two sides

If a completion or therapeutic axillary lymph node dissection is performed at the time of mastectomy, then the likelihood of the patient requiring postmastectomy radiation will be quite significant. It is anticipated that less than 5% of patients will be deemed ineligible on the basis of these 2 intra-operative exclusion criteria.

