##### ***Randomization***

Randomization will occur in during the pre-operative consult although the participant's final eligibility will be determined during surgery (see section on Eligibility). Patients will be randomized to undergo either ADM assisted one-stage reconstruction or two-stage reconstruction with TE placement without the use of ADM. The randomization allocation list will be developed by the Department of Epidemiology and Biostatistics at the University Health Network Research Institute. Sequentially numbered and sealed envelopes containing the treatment assignments will be prepared and given to the study coordinator in charge of the study site. Each envelope will contain two identical datasheets with the patient's name, medical record number and treatment assignment. One sheet will be returned to the study coordinator and the other sheet will be placed in the patient's chart.

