### **iib-10. Sample Size**

We consider clinically relevant change in the quality of life as a difference that exceeds half a standard deviation of the baseline value. Field-testing data of the Breast Q $\odot$  has found that the standard deviation of both the psychosocial function and satisfaction distributions is approximately 20. Thus, the minimum significant difference of score in each subscale is calculated to be 10. When we set our power at 85% with a  $\beta$  error of 0.1 and a standard  $\alpha$  error rate of 0.05, and applied the equation for equal sample sizes, we calculated a **minimum sample size of 72 patients per arm** for a total sample size of 144 patients. This sample size is also sufficient with power 84%,  $\alpha$  0.05, to detect a value of 0.06 for  $\eta^2$ , representing a medium effect size of the proportion of variability in the outcome variable (Breast Q $\odot$ ) that is explained by the independent variable(s), e.g., intervention.

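### One stated block length of eight, with arm counts printed by stratum, lets anyone tracking a stratum know up to one in five assignments before randomization

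*Combined protocol and SAP*

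**What the plan says.** - **Blocks and strata.** Section iia – 3 of the combined protocol and SAP says that the two arms have been balanced "in blocks of eight and is stratified by study site as well as laterality" of the reconstruction. The strata are laterality ("unilateral vs. bilateral reconstruction) at each of the three study sites"), so six in all. No other block length, and no varying length, is given anywhere.
- **Counts to date.** The same section states "Fifty-one patients have been randomized to date", prints the number per arm in each of the four Toronto strata, and reports 16 registered women still waiting to be randomized.
- **Concealment.** Section iib-4, Randomization: "Sequentially numbered and sealed envelopes containing the treatment assignments will be prepared and given to the study coordinator" at the site. A copy of each assignment goes into the patient's chart. No central allocation is described.
- **Gatekeeping.** Section iib-1: "Patients who are deemed eligible pre-operatively by the investigating surgeon for the study will be" randomized. Several criteria in iib-3 call for judgement, such as expected radiation, ptosis grade and desired breast volume.
- **Blinding.** Only the photograph panel (iib-8) is described as blinded. The primary outcome is a self-completed questionnaire.

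**The concern.** With a known, constant block length, the rest of a block is settled once one arm has used up its share. Nobody needs to open an envelope: the past assignments and the block length are enough. Past assignments are visible here because one arm has a second operation and the other does not, and because the chart holds the assignment sheet. The printed counts save even the effort of keeping a tally.

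Someone who knows the next assignment could bring a patient forward, defer her or steer her according to arm. That would make the arms differ at entry in ways related to the outcome. The exposure matters more than usual because the primary outcome is self-reported and no patient blinding is described. Motive is also plausible: section iia – 2 reports refusals over randomization and over the matrix, and says that two Vancouver surgeons had already done more than 35 one-stage cases.

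**Working it through.** The documents state no predictability figure, so there is none to reproduce.

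**Inputs.** Block length 8 (iia – 3). Equal allocation, since the arms are balanced and iib-10 "applied the equation for equal sample sizes"; hence 4:4 within a block, which is an inference. Six strata (iib-1). Planned total 144 (iib-10). Stratum counts from iia – 3.

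**1. One complete block.** There are C(8,4) = 70 equally likely orderings. After k assignments, one arm is already full with probability 2·C(k,4)/70.

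| Position | 1–4 | 5 | 6 | 7 | 8 |
|---|---|---|---|---|---|
| Probability that it is certain | 0 | 2/70 = 2.9% | 10/70 = 14.3% | 30/70 = 42.9% | 70/70 = 100% |

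Expected number certain = (2 + 10 + 30 + 70)/70 = 1.6 of 8, which is 20%.

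**2. The printed counts against 4:4 blocks.**

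| Stratum | One-stage : two-stage | Full blocks | Current block | What must follow |
|---|---|---|---|---|
| University Health Network, unilateral | 7 : 8 | 1 | 3 : 4 | next one is one-stage |
| University Health Network, bilateral | 10 : 8 | 2 | 2 : 0 | not determined |
| Women's College, unilateral | 2 : 2 | 0 | 2 : 2 | not determined |
| Women's College, bilateral | 8 : 6 | 1 | 4 : 2 | next two are two-stage |

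All four strata are compatible with 4:4 blocks of eight. Three upcoming assignments can be read from the table as it stood.

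**3. Allowing for unfinished blocks.** For the first 51 patients (strata of 15, 18, 4 and 14), the expected number certain is 2.2 + 3.2 + 0 + 1.77 = 7.17, and 7.17/51 = 14.1%. For example, 15 patients are one full block (1.6) plus positions 1–7 of the next (0.029 + 0.143 + 0.429 = 0.6). For 144 patients spread at random over six strata, simulation gives about 25 (17.5%), against 0.20 × 144 = 28.8 if every block were complete.

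**4. Effect of varying the block size.** Simulated for an observer who sees every past assignment and knows the set of sizes but not their order. Ranges cover assumed list lengths of 24 (144/6) and 144.

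| | Fixed 8 | Random 6, 8, 10 |
|---|---|---|
| Known with certainty | 20% | about 2% |
| More than 90% sure | 20% | about 3–4% |
| Best guess correct | about 67% | about 65–66% |

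Shorter fixed blocks would be worse: the certain share is 33% for blocks of 4 and 25% for blocks of 6.

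**The case against.** **Tracking.** The 20% needs someone who follows every assignment in the stratum. The coordinator holds the envelopes and the surgeon judges eligibility; these are different roles, and iia – 2 names three reconstructive surgeons at Vancouver alone. If a surgeon saw only half of the stratum's assignments (an assumption), the certain share would fall to about 1.2%. This stands as a limit on the size. It does not remove the point, because a team can keep a tally and the protocol itself prints one.

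**Timing and scope.** The block length appears once, as preliminary data on the two Toronto sites. Sections iib-1 and iib-4 give none. The document is dated 15 June 2011, Vancouver was due to join in January 2011, and accrual was expected to end in August 2011. A reader might infer that the Vancouver lists are unused and can simply be replaced; the documents do not show this.

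**Benefit.** Any better-than-chance guess can bias selection, and varied blocks hardly change guessing accuracy. This stands and must be said alongside the gain.

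**Analysis.** A reader might infer that no analysis could help. That is too absolute: baseline Breast Q enters the repeated-measures analysis (9c), and iib-7 lists adjustment covariates. Selection on measured factors can be partly addressed; selection on unmeasured ones cannot.

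**Before enrolment.** A reader might also infer that assignments are known before a woman enrols. The 16 women registered but not yet randomized show that registration came first in practice, so before randomization is the most that can be said.

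**Conclusion.** The point holds as a low-cost improvement to concealment, not as evidence of bias. Up to 20% of assignments are knowable with certainty before randomization. About 17.5% is the better figure for 144 patients in six strata, and 14% for the first 51. At the printed counts, three specific assignments were determined.

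These figures assume 4:4 blocks, one constant length and complete tracking within the stratum. Continued use of eights after the first 51 patients, and at Vancouver, is an inference, although no other scheme is described. Nothing in the documents shows that anyone used such foreknowledge, and a reader should not infer that anyone did.

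The intra-operative recheck should be kept apart. Exclusions such as "Patients who have significant mastectomy flap ischemia or asymmetry between the two sides" are applied after randomization, when the assignment is already known for every patient whatever the block length. It is tempting to cite this as support, but it is a separate exposure that changing the blocks would not cure.

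**What to change.** For any blocks not yet opened at any site, have the biostatistics department generate lists with randomly ordered block sizes, for example 6, 8 and 10. State in iib-4 only that block sizes vary. Keep the lengths, and running arm counts by stratum, out of every document held at a site. If no unopened blocks remain, only the second step still applies.

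The cost is a new set of envelopes and a slightly larger possible imbalance at the end of a stratum. Sample size, stratification and analysis are unchanged. The gain is the removal of nearly all certain assignments; it does not remove prediction in general.

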#### Preliminary cost-effectiveness analysis

The average piece of AlloDerm (LifeCell Corp, Branchburg, N.J.) for one-stage implant reconstruction is thick and 6cm X12cm in dimensions, and costs \$2105 in Canadian currency. Preliminary comparison of the two surgical techniques was performed by retrospectively reviewing all case costing data for 10 randomly selected study subjects who underwent either one-stage AlloDerm or two-stage TE/I reconstructions as part of the RCT from November 2009 to September 2010 through the University Health Network Accounting Department. Our hospital's Accounting Department collects cost data for every ambulatory clinic visit, emergency department visit, surgery, and in-hospital stay. We found that there were on average 5 more clinic visits (TE inflation sessions) in the two-stage TE/I than one-stage AlloDerm group. The average direct cost to the hospital was \$1,572 and \$595.91 more expensive per patient for the two-stage TE/I than AlloDerm assisted one-stage method for unilateral and bilateral reconstructions respectively. (APPENDIX 1)

#### Interim analysis of complication rates

An interim analysis of short-term complications revealed similar rates of postoperative complications between the two arms of the trial. In the one-stage AlloDerm assisted implant study arm, the rate of major complications is 0 and the rate of minor complications is 7%. There has been 1 case of cellulitis and 1 case of infected seroma both successfully treated with antibiotics. In the two-stage TE/I control arm, the rate of major complications is 4% and the rate of minor complications is 12.5%. In this arm, there were 2 cases of cellulitis successfully treated with antibiotics, 1 case of incisional dehiscence managed with conservative dressing changes, and 1 case of infected seroma that resulted in premature removal of the expander.

#### **iia – 4. Anticipated Impact**

Consistent with the mission of the American Society of Plastic Surgeons to “**provide the highest quality patient care**”, this proposal represents innovative research whose aim is to rigorously compare outcomes between a well-accepted method of breast reconstruction with a novel technique using a new biological material in the setting of a RCT. We are requesting funds to support a **cost-effectiveness analysis** to accompany this ongoing RCT. Unlike most biologic innovations that improve health outcome at an additional cost to the healthcare system, the use of ADM may be found to be cost-saving as indicated by our preliminary economic analysis (Preliminary cost effectiveness analysis). Even if it is not found to be cost-saving, the economic analysis may show that use of ADM is relatively economically attractive. Furthermore, the primary aim of the RCT is to find a better method of breast reconstruction from the **patient perspective** in addition to the traditional assessments of outcomes such as complication rates and aesthetic results from a surgeon's perspective. This primary outcome will be measured using the Breast Q©, a prospectively designed and validated patient reported outcome questionnaire for breast reconstruction. Lastly, since the TE/I reconstructive method is performed routinely in community hospitals as well as teaching hospitals, research directed at improving implant reconstructive techniques has the potential to impact the most common practice in breast reconstruction and QOL of breast cancer survivors throughout North America.

